#### ***4.6 Early Termination of the Clinical Trial***

Sponsor reserves the right to discontinue the Clinical Investigation at any stage, with suitable written notice to the investigator. The investigator may also discontinue participation in the Clinical Investigation with suitable written notice to Sponsor. Should either of these events occur, the investigator shall return all documents and devices to the Sponsor, provide a written statement as to why the premature termination has taken place, and notify the Ethics Committee and the regulatory authority (if applicable). All applicable Clinical Investigation documents shall be subject to the same retention policy as detailed in the **Section 13.0** Data Handling and Record Keeping.

All subjects registered up to the point of trial discontinuation will continue to be followed up per protocol requirements.

### **5. ENDPOINTS**

#### ***5.1 Primary Endpoint***

##### **ABSORB III Primary Endpoint**

1. TLF at 1 year, non-inferiority (NI) against the control.

- TLF is defined as composite of Cardiac Death, Myocardial Infarction (per protocol-defined MI definition, Appendix II) attributable to Target Vessel (TV-MI), or Ischemia-Driven Target Lesion Revascularization (ID-TLR).
- This analysis will include ~2000 subjects.

#### ***5.2 Powered Secondary Endpoint(s)***

##### **Imaging Cohort Powered Secondary Endpoints**

Imaging Cohort Powered Secondary Endpoints are based on the pooled subjects from the Imaging Cohort of Absorb III (~ 200 angiographic subjects and ~150 IVUS subjects) and subjects from the Absorb Japan RCT (~ 400 angiographic subjects, and ~150 IVUS subjects).

One of the key attributes that differentiates Absorb BVS from metallic stents is the progressive mechanical weakening of the scaffold with polymer degradation over time, which allowed for vessel movement and gradual outward remodeling (positive) to accommodate any increases in the in-scaffold intimal hyperplasia that may limit blood flow. In both the Absorb Cohort A and Cohort B trials, Absorb BVS treated vessels have shown evidence of vessel movement and late lumen and scaffold enlargement, providing anatomic indication that the vessel can adapt and enable the natural Glagov process.

The vasomotion endpoint assesses the ability of the in-scaffold segment to move when the vessel is no longer mechanically constrained. Angiography will be used for the vasomotion assessment. The assessment of late lumen enlargement will be evaluated by the in-stent/scaffold mean lumen area change ( $\Delta$ MLA) from post-procedure to 3 years by IVUS.

1. The in-stent/scaffold mean lumen area change, from post-procedure to 3 years by IVUS (mean lumen area measured after nitrate infusions, superiority test, ~300 pooled subjects).
2. The in-stent/scaffold mean lumen diameter change, between pre- and post-nitrate infusion at 3 years by angiography (superiority test, ~600 pooled subjects).

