### Imaging Cohort

A prospective, randomized (2:1 Absorb BVS to XIENCE), single-blind, multi-center cohort, registering approximately 200 subjects. The 200 subjects are separate from the 2000 subjects included in the primary endpoint analysis. The objective of the Imaging Cohort is to evaluate long-term vascular function and patency of the Absorb BVS treated segments compared to XIENCE treated segments. Data from two powered secondary endpoints from this cohort will

 The commercially approved CE marked device will be used in geographies where it is commercially available.

 The Absorb™ Bioresorbable Vascular Scaffold (BVS) System is the trade name for this product. During the course of development, multiple product names were used to describe this product including, Bioresorbable Vascular Scaffold (BVS) System, Bioabsorbable Vascular Stent, BVS Everolimus Eluting Coronary Stent System (EECSS), Abbott Vascular Bioabsorbable Device (AVBD) EECSS, BVS Cohort A (used in the ABSORB Cohort A trial) and BVS Cohort B (used in the ABSORB Cohort B trial).

Confidential and Proprietary

[figure not shown]
Do not distribute or reproduce without the prior written permission of Abbott Vascular Inc.

ABSORB III Randomized Control Trial Version 17.0 August 16, 2018.

support label claims of superiority of Absorb BVS as compared to XIENCE specific to vasomotion and late lumen enlargement.

After the completion of Lead-In Phase, enroll/registration of the 2000 subjects for the primary analysis and the 200 subjects in the Imaging Cohort will begin. All trial elements will apply to Lead-In Phase and the Imaging Cohort, unless otherwise specified.

**Figure 1.1** provides the complete ABSORB III design.

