#### **Imaging Cohort Powered Secondary Endpoint 1**

The in-stent/scaffold mean lumen area change ( $\Delta$ MLA) from post-procedure to 3 years by IVUS (mean lumen area is to be measured after nitrate infusions) will be evaluated using the difference between the two means of the two treatment arms in the pooled subjects from the Imaging Cohort of ABSORB III and ABSORB Japan. Superiority testing will be performed with a two-sided alpha of 0.05. The null ( $H_0$ ) and alternative ( $H_A$ ) hypotheses for the superiority test are:

$$H_0: \Delta\text{MLA}_{\text{Absorb}} - \Delta\text{MLA}_{\text{XIENCE}} = 0$$

$$H_A: \Delta\text{MLA}_{\text{Absorb}} - \Delta\text{MLA}_{\text{XIENCE}} \neq 0.$$

$\Delta\text{MLA}_{\text{Absorb}}$  and  $\Delta\text{MLA}_{\text{XIENCE}}$  are the in-stent/scaffold mean lumen area changes in the Absorb BVS and XIENCE arms, respectively.

The sample size calculation is based on the following assumptions:

- The in-stent/scaffold mean lumen area change at 3 years for the Absorb BVS arm is assumed to be  $0.5 \pm 1.69 \text{ mm}^2$
- The in-stent/scaffold mean lumen area change at 3 years for the XIENCE arm is assumed to be  $-0.4 \pm 1.17 \text{ mm}^2$
- Two-sided alpha= 0.05
- $\sim 150$  subjects from the Imaging Cohort in ABSORB III, 50% IVUS follow-up rate at 3 years

- ~150 subjects from ABSORB Japan, 70% IVUS follow-up rate at 3 years
- ~15% of all subjects will have dual target lesion treatment.

An effective sample size of 207 lesions (138 for the Absorb BVS arm and 69 for the XIENCE arm) will provide approximately 99.4% power using two sample t-test.

The sample size calculation was performed using NCSS PASS 2008 (Hintze JL, 2002. PASS User's Guide-II. NCSS).

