#### **10.4.2 Powered Secondary Endpoint Analyses**

Analysis of the Powered Secondary Endpoints for angina, for all revascularization, for ID-TVR, and for diabetic indication will include subjects from the primary analysis group. Pearson's Chi-square test will be used for superiority testing based on the ITT and PTE populations for the powered secondary endpoint for angina. Fisher's exact test will be used for superiority testing based on the ITT and PTE populations for the powered secondary endpoints for all revascularization and for ID-TVR. Analysis of the Imaging Cohort Secondary Endpoints 1 and 2 will include pooled subjects from the Imaging Cohort of ABSORB III and ABSORB Japan. Two sample t-test will be used for superiority testing based on the ITT and PTE populations.

Details of the analyses for the powered secondary endpoints can be found in the statistical analysis plan (SAP).

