### **16.3 Potential Benefit**

The Absorb BVS is intended to revascularize the vessel like a conventional metallic stent, provide controlled elution of anti-proliferative drug to minimize neointimal growth and then resorb naturally into the body after vessel healing and remodeling are complete.

The imaging and vasomotion data from ABSORB Cohort A at 2 years and ABSORB Cohort B at 1 year showed the potential for vessel movement with the ABSORB BVS in response to pharmacological stimuli (**Section 2.1.9**). Lumen patency was maintained as shown with an increase in IVUS average lumen area in ABSORB Cohort A at 2 years and maintained average lumen area in ABSORB Cohort B at 2 years (**Section 2.1.9**).

Another benefit of Absorb BVS is that non-invasive imaging can be done using multislice computed tomography (MSCT) to evaluate stenosis of treated lesion. The Absorb BVS scaffold is radiolucent and was undetected by MSCT apart from the platinum markers at each end of the scaffold. In 24 subjects of ABSORB Cohort A, the scaffolded vessel segment at 2 years were

qualitatively patent. The 18-month clinical and MSCT results for the full ABSORB Cohort B trial (Cohort B1 and B2, 101 patients) were reported at the TCT congress in November, 2011. Unlike metal stents, on MSCT scans at 18 months it was possible to assess quantitatively the scaffolded segment in 61 of the 72 scans performed. These results provided an early indication that non-invasive imaging is feasible with the Absorb BVS System, which could reduce patient burden.

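### The powered IVUS endpoint is to support a late lumen enlargement claim, but its between-arm test does not show that the Absorb lumen enlarged

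*Combined protocol and SAP*

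**What the plan says.** ABSORB III Section 5.2 makes the IVUS change in mean lumen area, from post-procedure to 3 years, the measure of late lumen enlargement: "The assessment of late lumen enlargement will be evaluated by the in-stent/scaffold mean lumen area change". The Protocol Summary (Study Design) and Section 1 (Imaging Cohort) say that the imaging data will "support label claims of superiority of Absorb BVS as compared to XIENCE specific to vasomotion and late lumen enlargement".

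The decision rule is in Section 10.3.2, Imaging Cohort Powered Secondary Endpoint 1. The null hypothesis is that the two arms have equal mean change. "Superiority testing will be performed with a two-sided alpha of 0.05". Planning values are +0.5 ± 1.69 mm² for Absorb and -0.4 ± 1.17 mm² for XIENCE, and "An effective sample size of 207 lesions (138 for the Absorb BVS arm and 69 for the XIENCE arm) will provide approximately 99.4% power". Section 10.4.2 names the analysis: "Two sample t-test will be used for superiority testing based on the ITT and PTE populations". It does not say whether the equal-variance or the unequal-variance form is meant.

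The protocol nowhere makes the Absorb arm's own change a condition of the conclusion. Section 10.4 provides means and 95% confidence intervals for continuous variables, and Section 5.3 lists the percentage of subjects with late gain by IVUS. Section 10.4.3 treats secondary endpoints other than the powered ones as descriptive.

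**The concern.** Superiority in late lumen enlargement asserts two things: that Absorb did better than XIENCE, and that the Absorb lumen enlarged. The t-test addresses only the first. Because the plan itself expects XIENCE to lose lumen, a significant difference can come from control-arm loss while Absorb merely holds its post-procedure area. The accurate conclusion would then be less late lumen loss than XIENCE.

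The protocol's own data leave this possibility open. In Table 2.3 (Section 2.1.9), Cohort B Group 1 mean lumen area was 6.53 mm² post-procedure, 6.36 at 6 months and 6.85 at 2 years. The rise from 6 months has p = 0.0105. The rise from post-procedure, which is the baseline used for this endpoint, has p = 0.3515. Section 16.3 describes the finding as "maintained average lumen area in ABSORB Cohort B at 2 years".

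What is at stake is the wording of a powered, label-supporting secondary conclusion. Study success rests on 1-year TLF and is not affected.

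**Working it through.** **Inputs** (Section 10.3.2): means +0.5 and -0.4 mm²; SDs 1.69 and 1.17; 138 and 69 lesions; two-sided alpha 0.05. The lesion count follows from the follow-up assumptions: 150 × 0.5 + 150 × 0.7 = 180 subjects, and 180 × 1.15 = 207 lesions, split 2:1. Counting one lesion per subject gives 120 and 60.

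**1. Reproduce the stated power.**
- SE = √(1.69²/138 + 1.17²/69) = √(0.02070 + 0.01984) = 0.2013.
- 0.9/0.2013 = 4.470; Φ(4.470 − 1.960) = 99.4%.
- The unequal-variance (Welch) t calculation gives 99.36%. The stated 99.4% is reproduced. A pooled-variance formula gives 97.8%, so Welch is the closer match.

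**2. What the rule requires.** With the planned SDs, significance needs an observed difference of about 1.973 × 0.2013 = 0.40 mm². That equals the loss assumed for XIENCE alone.

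**3. Set Absorb's true mean change to 0 and leave everything else as planned.** This value is an assumption, not a figure in the protocol. The true difference is then 0.4 mm². By the normal approximation, 0.4/0.2013 = 1.987 and Φ(1.987 − 1.960) = 51.1%. The chance of a significant result in Absorb's favour is:

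| Sample | Welch | Pooled variance |
|---|---|---|
| 138/69 lesions | 51% | 41% |
| 120/60 subjects | 45% | 36% |

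The pooled figures come from simulation with the planned unequal SDs. In the 138/69 Welch case, about 13% of all trials are won with an observed Absorb mean at or below 0. That is about a quarter of the wins (0.13/0.51).

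**4. Add a within-Absorb condition: lower two-sided 95% limit of the mean change above 0.** The Absorb SE is 1.69/√138 = 0.144, so the observed Absorb mean must exceed about 1.977 × 0.144 = 0.28 mm². Simulated Welch results with 138/69 lesions:

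| True Absorb change (mm²) | Between-arm test won | Both conditions met |
|---|---|---|
| +0.5 (planned) | 99.4% | 93% |
| +0.32 (Cohort B, 6.85 − 6.53) | 94% | about 60% |
| 0 | 51% | 2.4% |

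Under the planned +0.5 with 120/60, both conditions are met in 89%.

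**The case against.** The strongest reply is that the claim is comparative. It is worded as superiority over XIENCE, Section 5.2 defines the measure, and a between-arm difference in that measure is what randomisation protects. This stands for the comparative half of the claim, and it is why the t-test should remain the powered test. It does not supply the other half, that enlargement occurred.

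A reader might infer that 51% is a false-positive rate. It is not. With Absorb at 0 and XIENCE at -0.4 the null hypothesis is false, and rejecting it is correct. The figure is power for a true difference of 0.4 mm². It is also the highest of the four variants, and it is conditional on first passing TLF non-inferiority and the testing sequence described in Section 10.3.2.

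A reader might also infer that the test is usually won while the Absorb data show no growth. At a true change of 0, a win with an observed mean at or below 0 occurs in about 13% of trials. At +0.32 it is about 0.5%, and at the planned +0.5 about 0.01%.

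Nor does Cohort B show that Absorb fails to enlarge. The post-procedure comparison rests on 33 subjects with a point estimate of +0.32 mm² at 2 years. Scaffold area (p = 0.0035) and vessel area (p < 0.0001) did rise from post-procedure. These data make a zero change possible; they do not establish it at 3 years.

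Two further points stand. Readers will see the within-arm means and intervals in any case. The separate SAP, to which the protocol defers details, is not reproduced here and may already contain a within-arm condition.

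**Conclusion.** The between-arm test is sound for superiority in lumen area change. By itself it does not support a statement that the Absorb lumen enlarged from the post-procedure baseline. If Absorb's true change were 0, the test would be significant in about 36% to 51% of the trials that reach it. The range reflects the unspecified t-test form and the choice between lesions and subjects, and it rests on the planned XIENCE mean and both planned SDs. The gap concerns how a powered secondary result is worded. It does not concern the validity of the test or trial success, and the protocol does not support calling the 51% an error rate. Correcting the wording rule is worthwhile because the result is intended for the label.

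**What to change.** Keep the between-arm t-test and its 99.4% power as the powered superiority test. Add to Sections 5.2, 10.3.2 and 10.4.2:

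- A significant result in Absorb's favour is described as late lumen enlargement only if the lower two-sided 95% confidence limit of the Absorb arm's mean change from post-procedure to 3 years is also above 0 mm².
- If only the between-arm test is significant, the result is reported as a more favourable lumen area change (less late lumen loss) than XIENCE.

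Both conditions must hold for the enlargement wording, so no alpha adjustment is needed. State the joint power for that wording: about 93% under the planned +0.5 mm², or 89% with 120/60. If the separate SAP already contains such a condition, cite it in these sections instead.

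The cost is a short addition to the text and no new data, since Section 10.4 already provides the interval. There is a real downside: if the true gain is only the Cohort B 2-year value of +0.32 mm², the enlargement wording would be reached in about 60% of trials, although the comparative result would be significant in about 94%.

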### **Powered Secondary Endpoint for Angina**

This powered secondary endpoint is intended to assess angina at 1 year and test for superiority of Absorb BVS to XIENCE.

- Angina is defined as the first adverse event resulting in the site diagnosis of angina.
- The analysis will exclude angina following the index procedure through discharge, not to exceed a period of 7 days.

This analysis will include ~2000 subjects.

### **Powered Secondary Endpoint for All Revascularization**

This powered secondary endpoint is intended to assess all revascularization at 1 year and test for superiority of Absorb BVS to XIENCE.

This analysis will include ~2000 subjects.

### **Powered Secondary Endpoint for Ischemia-Driven Target Vessel Revascularization**

This powered secondary endpoint is intended to assess ischemia-driven target vessel revascularization at 1 year and test for superiority of Absorb BVS to XIENCE.

---

This analysis will include ~ 2000 subjects.

### **Powered Secondary Endpoint for Diabetic Indication**

The powered secondary endpoint will be to support a diabetic indication for Absorb BVS.

### **5.3 Additional Secondary Endpoint(s)**

In ABSORB III the following clinical secondary endpoints will be analyzed. Secondary imaging endpoints will be analyzed in the Imaging Cohort.

- **Acute Success:** (Combined Clinical/Angiographic Endpoint)
  - Device success (Lesion level analysis)
  - Procedural success (Subject level analysis)
- **Clinical Endpoint** in hospital and at each follow-up point (30 days; 180 days; 1, 2, 3, 4 and 5 years).
  - **Component**
    - Death (Cardiac, Vascular, Non-cardiovascular)
    - Myocardial Infarction
      - Attributable to target vessel (TV-MI)
      - Not attributable to target vessel (NTV-MI)
    - Target Lesion Revascularization (TLR)
      - Ischemia driven TLR (ID-TLR)
      - Non ID TLR (NID-TLR)
    - Target Vessel Revascularization (TVR,
      - ID TVR
      - Non ID TVR
    - All coronary revascularization
  - **Composite Endpoints**
    - Death/All MI
    - Cardiac Death/All MI
    - Cardiac Death/TV-MI/ID-TLR (TLF)

- Cardiac Death/All MI/ID-TLR (MACE)
- Cardiac Death/All MI/ID-TLR/ID-TVR, non TL (Target Vessel Failure, TVF)
- Death/All MI/All revascularization
- **Scaffold-Thrombosis / Stent Thrombosis (per ARC definition)**
  - Timing (acute, sub-acute, late and very late)
  - Evidence (Definite and Probable)
- **Imaging Endpoints:**

Imaging endpoints will be analyzed on Imaging Cohort subjects only.

○ **Angiography:**

All angiographic endpoints will be collected post-procedure and at 3 years

- In-segment late loss (LL)
- In-device LL
- Proximal LL (proximal defined as 5 mm of tissue proximal to the device placement)
- Distal LL (distal defined as 5 mm of tissue distal to the device placement)
- In-device/in-segment/proximal/distal minimum lumen diameter
- In-device/in-segment/proximal/distal %Diameter Stenosis (DS)
- In-device/in-segment/proximal/distal angiographic binary restenosis
- In-device net gain (change in minimum lumen diameter between 3 years and post-procedure)
- The magnitude of in-stent/scaffold mean lumen diameter change (absolute value) at 3-years follow-up from pre-nitrate to post-nitrate
- The normalized in-stent/scaffold mean lumen diameter change at 3-years follow-up from pre-nitrate to post-nitrate, defined as,

$$\frac{\text{In - Stent/Scaffold Mean Lumen Diameter change}}{(\text{Proximal Mean Lumen Diameter change} + \text{Distal Mean Lumen Diameter change})/2} \times 100\%$$

 In-device refers to the margins of the stent or scaffold. Segment refers to the margins of the stent or scaffold and 5 mm proximal and 5 mm distal to the stent or scaffold.

 Device throughout the protocol summary refers to XIENCE or Absorb BVS System

Confidential and Proprietary

Do not distribute or reproduce without the prior written permission of Abbott Vascular Inc.  
ABSORB III Randomized Control Trial Version 17.0 August 16, 2018.

where both proximal and distal mean lumen diameter changes are at 3-years follow-up from pre-nitrate to post-nitrate

- Change in minimum lumen diameter, within treated segment, at 3 years follow-up from pre-nitrate to post-nitrate
- Change in in-device %DS at 3 years follow-up from pre-nitrate to post-nitrate

- **IVUS (Grey scale):**

All IVUS endpoints will be collected post-procedure and at 3 years (as applicable) and within the device and within the treated segment:

- Minimal Lumen Area
- Percentage of subjects with late gain without incomplete apposition by IVUS (IVUS minimum lumen area post- procedure post-nitrate - IVUS minimum lumen area 3 years follow-up post-nitrate)
- % change in the tissue area/volume between lumen and external elastic lamina (EEL)
- Absolute change in tissue area/volume between lumen and EEL
- Mean/minimal vessel diameter/area/volume
- Mean/minimal device diameter/area/volume; if analyzable in respect to Absorb BVS
- Mean/minimal lumen diameter/area/volume, including change in minimum lumen area between post-procedure and follow-up
- Mean/maximal neointima hyperplasia area/volume/percentage at 3 years; if analyzable in respect to Absorb BVS
- Incomplete apposition (post-implantation), persisting incomplete apposition, late acquired incomplete apposition and resolved incomplete apposition at 3 years; if analyzable in respect to Absorb BVS

- **OCT:**

All OCT endpoints will be collected post-procedure and 3 years, and for within the device and within the treated segment:

- Descriptive analysis of strut, lesion and vessel morphology
- Mean neointimal area (NIA)
  - Apposed to the vessel wall with neointimal coverage
  - Apposed to vessel wall without neointimal coverage

- Incomplete apposition to vessel wall with neointimal coverage
- Incomplete apposition to vessel wall without neointimal coverage
- Lumen area/volume stenosis %
- Mean/minimal device area
- Mean/minimal luminal area/volume
- Mean strut area/volume
- Persisting incomplete apposition, late incomplete apposition at 3 years (if analyzable)
- OCT analysis for subjects with jailed side branch
- Descriptive analyses from 3-dimensional OCT reconstructions

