### **Imaging Cohort Powered Secondary Endpoint 2**

The in-stent/scaffold mean lumen diameter change ( $\Delta$ MLD) between pre- and post-nitrate infusion at 3 years by angiography will be evaluated using the difference between the means of the two treatment arms in the pooled subjects from the Imaging Cohort of ABSORB III and ABSORB Japan. Superiority testing will be performed with a two-sided alpha of 0.05. The null ( $H_0$ ) and alternative ( $H_A$ ) hypotheses for the superiority test are:

$$H_0: \Delta\text{MLD}_{\text{Absorb}} - \Delta\text{MLD}_{\text{XIENCE}} = 0$$

$$H_A: \Delta\text{MLD}_{\text{Absorb}} - \Delta\text{MLD}_{\text{XIENCE}} \neq 0.$$

$\Delta\text{MLD}_{\text{Absorb}}$  and  $\Delta\text{MLD}_{\text{XIENCE}}$  are the in-stent/scaffold mean lumen diameter changes in the Absorb BVS and XIENCE arms, respectively.

The sample size calculation is based on the following assumptions:

- The in-stent/scaffold mean lumen diameter change at 3 years for the Absorb BVS arm is assumed to be  $0.054 \pm 0.156$  mm (based on 3-year imaging data from the Absorb Cohort B trial).
- The in-stent/scaffold mean lumen diameter change at 3 years for the XIENCE arm is assumed to be  $0.018 \pm 0.052$  mm (based on clinical assumptions as no imaging data for XIENCE is available)
- Two-sided alpha= 0.05
- ~200 subjects from the Imaging Cohort in ABSORB III, 50% angiographic follow-up rate at 3 years
- ~400 subjects from ABSORB Japan, 80% angiographic follow-up rate at 3 years
- ~15% of all subjects will have dual target lesion treatment

An effective sample size of 483 lesions (322 for the Absorb BVS arm and 161 for the XIENCE arm) will provide approximately 96.2% power using two sample t-test.

The sample size calculation was performed using NCSS PASS 2008 (Hintze JL, 2002. PASS User's Guide-II. NCSS).

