#### **10.4 Statistical Analyses**

Non-inferiority testing of the primary endpoints will be one-sided and performed at a 0.025 significance level for the comparison of the Absorb BVS arm with the XIENCE arm. Superiority tests on the powered secondary endpoints will be performed at a two-sided 0.05 significance level. Analyses of other secondary endpoints will be descriptive in nature.

For binary variables such as TLF, TLR, and clinical procedure success, counts, percentages, and 95% confidence intervals will be calculated, and p-values may be presented for hypothesis generating purposes. Pearson's Chi-squared test or Fisher's exact test will be performed when appropriate. In addition, logistic regression will be performed to determine whether the baseline characteristics exhibit any trends in predicting TLF.

For continuous variables such as age, means, standard deviations, and 95% confidence intervals for the mean will be calculated and p-values may be presented for hypothesis generating purposes. For time-to-event variables, such as time to TLF, survival curves will be constructed using Kaplan-Meier estimates, and log rank test results will be displayed. Unless specified, analyses will be performed with pooled data across all study sites.

For further details refer to the statistical analysis plan (SAP).

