#### **10.4.3 Secondary Endpoint Analyses**

Secondary endpoints other than the powered endpoints described above will be summarized descriptively for the ITT population. For further details refer to the statistical analysis plan (SAP).

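### The normalised vasomotion endpoint divides by a signed reference response with no denominator rule, so a mean of per-lesion ratios can misorder lesions and be unstable

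*Combined protocol and SAP*

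**What the plan says.** ABSORB III Section 5.3 (Angiography) lists "The normalized in-stent/scaffold mean lumen diameter change at 3-years follow-up", from before to after nitrate, defined as the in-stent/scaffold change over the mean of the proximal and distal changes, times 100%. The only further condition concerns timing: "where both proximal and distal mean lumen diameter changes are at 3-years follow-up from pre-nitrate to post-nitrate". The section does not say what to do with a zero, small or negative denominator. It does not name a summary measure, and it does not state whether the ratio is formed per lesion or per arm.

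The analysis set is given in the same section: "Imaging endpoints will be analyzed on Imaging Cohort subjects only". Section 10.4.3 sets the status: "Secondary endpoints other than the powered endpoints described above will be summarized descriptively for the ITT population". The general rule in Section 10.4 is: "For continuous variables such as age, means, standard deviations, and 95% confidence intervals for the mean will be calculated".

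Section 7.3.8.4 (Vasomotion Assessment) lists conditions under which vasomotion is not assessed: metallic overlap, intervening PCI, and a flow-limiting stenosis that needs treatment. None of them concerns the response of the adjacent segments.

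The powered vasomotion endpoint (Sections 5.2 and 10.3.2, Imaging Cohort Powered Secondary Endpoint 2) is the un-normalised change. It does not use this ratio.

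**The concern.** Numerator and denominator are both signed changes. Taken per lesion, which is the natural reading, the ratio has two faults that need no numerical assumption.

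- A lesion that dilates in the device and in the reference segments gets the same positive percentage as one that constricts in both.
- A scaffold that dilates beside slightly constricting reference segments gets a negative score.

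The value therefore does not order lesions by restored vasomotion. In addition, a denominator close to zero produces a very large ratio of either sign. If such denominators occur, a few lesions fix the arm mean and its confidence interval.

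At stake is the only listed angiographic endpoint that scales the device response to the adjacent segments of the same vessel. No hypothesis test or power statement depends on it.

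**Working it through.** **The plan's own figures.** Section 10.3.2 assumes in-device changes of 0.054 mm (SD 0.156) for Absorb, "mm (based on 3-year imaging data from the Absorb Cohort B trial", and 0.018 mm (SD 0.052) for XIENCE, the latter a clinical assumption.

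- Lesions: (200 × 0.50 + 400 × 0.80) × 1.15 = 483, split 322 to 161.
- SE = √(0.156²/322 + 0.052²/161) = 0.00961, and 0.036/0.00961 = 3.75.
- Power with unequal variances is 96.2% by the noncentral t. This matches the stated 96.2%.

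These figures concern the un-normalised endpoint. None is stated for the ratio.

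**Analysis set for the ratio.** It uses the ABSORB III Imaging Cohort only: 200 × 0.50 × 1.15 = 115 lesions, about 77 Absorb and 38 XIENCE at 2:1. The 322 lesions belong to the analysis pooled with ABSORB Japan and do not apply here.

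**Sign behaviour (illustration).** Take the planned response of 0.054 mm and reference changes of ±0.15 mm or -0.01 mm.

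- +0.054/+0.15 = 36%
- -0.054/-0.15 = 36%
- +0.054/-0.01 = -540%

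**Denominator (assumed).** The documents give no mean or SD for the proximal or distal change. Suppose that each is normal with mean μ and SD s, uncorrelated. Then the denominator has SD s/√2 and P(denominator ≤ 0) = Φ(-μ√2/s). For μ = 0.054 and s = 0.156, the SD is 0.110, and Φ(-0.49) = 31%, or about 24 of 77 lesions.

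**Simulation.** Each run has 77 Absorb lesions. The numerator is normal (0.054, SD 0.156) and independent of the denominator. Entries are the 95% range of the Absorb arm summary.

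| Reference mean, SD (mm) | Denominator ≤ 0 | Within 0.02 mm of zero | Mean of per-lesion ratios | Ratio of arm means |
|---|---|---|---|---|
| 0.054, 0.156 | 31% | 13% | about -1800% to +2000% | 33% to 222% |
| 0.15, 0.156 | 9% | 6% | about -660% to +720% | 13% to 61% |
| 0.15, 0.10 | 2% | 2.5% | about -290% to +380% | 13% to 61% |
| 0.15, 0.052 | about 0% | about 0% | 11% to 66% | 12% to 59% |

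The wide limits differ between simulation runs, as expected for a mean driven by extreme values. For the first row, two other runs gave -1671% to +1624% and -1758% to +1530%. The stable row barely moves (12% to 66% and 12% to 65%).

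A correlation of 0.5 between the proximal and distal changes alters little: -1395% to +1474% in the first row and 6% to 77% in the last. A correlation of 0.5 between numerator and denominator does not remove the instability.

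**Does the replacement work at this size?** A Fieller interval is bounded when the reference mean exceeds about 1.96 of its standard errors. In the least favourable row of the table, the expected values are 0.054/(0.110/√77) = 4.3 for Absorb and 0.054/(0.110/√38) = 3.0 for XIENCE.

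**The case against.** A reader might infer that denominators are in fact often near zero or negative, so that the arm means are meaningless. The documents do not support that. The low ratio of mean to SD in Section 10.3.2 (0.054/0.156 = 0.35) describes the in-device response, which is the numerator. Nothing is reported for adjacent native vessel. With a reference mean of 0.15 mm and SD of 0.052 mm, or 0.20 mm and SD 0.052 mm (9% to 46%), the mean of ratios is stable. This objection stands, and the instability is therefore stated conditionally.

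A reader might also infer that the vasomotion label claim is at risk. It is not. The protocol summary ties that claim to the powered endpoint data. Section 5.3 also lists un-normalised nitrate responses: absolute change, change in minimum lumen diameter and change in percent stenosis.

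The mean-and-interval rule in Section 10.4 is generic, and the per-lesion unit is inferred. Sections 10.4 and 10.4.3 refer to the SAP for details, and Section 7.3.8.4 refers to the Imaging Guidance Document. A denominator rule could be there, but neither document's content is in the text reviewed. This limits the point to the protocol as written.

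The sign problem is not answered by any of this. It follows from the definition itself. The stable case at 0.15 mm also needs free adjacent vessel to vary as little as the SD assumed for a metal-stented segment, 0.052 mm. That is possible, but it is not a safe basis for planning.

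**Conclusion.** The point holds in conditional form. As defined and read per lesion, the endpoint does not order lesions by vasomotion, and the protocol text provides neither a denominator rule nor an endpoint-specific summary.

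Whether the arm mean is also unstable depends on reference-segment means and SDs that the documents do not give. Over the cases tabulated, it ranges from unusable (95% range of thousands of percent) to stable (11% to 66%). Even about 2% of denominators at or below zero, between one and two of 77 lesions, widens the range to about -290% to +380%. The ratio of arm means was much tighter in every unstable case and similar in the stable one.

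These figures assume normal responses, a common mean and SD for the two reference segments, and the planned Absorb response and follow-up rate. The importance is minor: the endpoint is non-powered and descriptive, and the powered vasomotion test does not use it.

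**What to change.** State in the SAP that this endpoint is summarised in each arm as the mean in-device change divided by the mean reference change (the average of proximal and distal), with a Fieller or bootstrap 95% interval. As an alternative, compare arms by ANCOVA of the in-device change on the mean reference-segment change.

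- Report the median per-lesion ratio descriptively only, with the number of lesions whose denominator is zero or negative.
- Resample subjects rather than lesions in a bootstrap, because about 15% of subjects are planned to have two target lesions.
- If the reference mean in an arm is not clearly above zero, the Fieller interval may be unbounded. The ANCOVA result should then be the one reported.

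The cost is a few sentences of SAP wording. The same measurements are used, and sample size and the powered tests do not change. If the SAP or the Imaging Guidance Document already contains a denominator rule and a summary measure, cite it in Section 5.3 and check it against the sign problem above.
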